8.4 Detection of Bias

This study has been designed to minimize potential bias using randomization of subjects into treatment groups and the use of blinding. Other factors that may bias the results of the study include:

- major protocol deviations likely to impact the analysis and interpretation of the efficacy endpoints
- subject level unblinding before final database lock and formal unblinding

Important protocol deviations likely to impact the analysis and interpretation of the efficacy endpoints will be tabulated in the Clinical Study Report (CSR). Any unblinding of individual subjects prior to formal unblinding of the study will be documented in the CSR.

8.5 Outliers

Various methods, including univariate summaries, histograms, scatter plots, box plots, and line graphs, may be used to identify outliers in key safety and efficacy variables. The primary analyses will include outliers in the data. Sensitivity analyses may be undertaken if extreme outliers for a variable are observed.

8.6 Distributional Characteristics

If the distributional assumptions are not met, then alternative methods will be utilized. The use of alternative methods will be fully justified in the CSR.

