10.3.2.2 Efficacy Analyses

Endpoint	Statistical Analysis Methods
Primary	The primary analysis method of the primary endpoint is to use the analysis of covariance (ANCOVA) model, including terms for treatment group, stratification factor (current statin use [> 4 weeks or ≤ 4 weeks] at randomization), and baseline FCT as covariates. Least square means and corresponding 95% confidence intervals will be calculated for each treatment group and for the difference between the treatment groups. For subjects with missing post-baseline FCT, the missing primary endpoint will be imputed using multiple imputation (details provided in SAP). FAS will be used. A sensitivity analysis of the primary endpoint will be conducted using nonparametric method and FAS.
Secondary	ANCOVA model including terms for treatment group, stratification factor (current statin use [> 4 weeks or ≤ 4 weeks] at randomization), and respective baseline value as covariates.
Exploratory	Will be described in the statistical analysis plan finalized before database lock

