2.1 Objectives and Endpoints

Objectives	Endpoints
Primary	

 To evaluate the effect of evolocumab on fibrous cap thickness (FCT) in subjects with non-ST-elevation acute coronary syndrome (NSTEMI-ACS) who are taking maximally tolerated statin therapy. 	
 Absolute change in minimum FCT in a matched segment of artery as determined by optical coherence tomography (OCT) from baseline to week 50.
Secondary	

 To evaluate the effects of evolocumab on coronary plaque morphology in subjects with NSTEMI-ACS who are taking maximally tolerated statin therapy. 	
 Coronary artery segment-based: 
 Percent change in minimum FCT in a matched segment of artery as determined by OCT from baseline to week 50. Absolute change in mean minimum FCT for all images assessed in an individual subject as determined by OCT from baseline to week 50. Absolute change in the maximum lipid arc in a matched segment of artery as determined by OCT from baseline to week 50. Plaque-based: 
 Absolute change in minimum FCT in lipid rich plaques defined as minimum FCT < 120 µm and lipid arc > 90° in at least 3 consecutive images as determined by OCT from baseline to week 50. Absolute change in maximum lipid arc in lipid rich plaques defined as minimum FCT < 120 µm and lipid arc > 90° in at least 3 consecutive images as determined by OCT from baseline to week 50. Absolute change in lipid core length in

Objectives	Endpoints
Secondary(Continued)	
	
 lipid rich plaques defined as minimum FCT < 120 µm and lipid arc > 90° in at least 3 consecutive images as determined by OCT from baseline to week 50.
Safety	

 To evaluate the safety and tolerability of evolocumab treatment in subjects with NSTEMI-ACS who are taking maximally tolerated statin therapy. 	
 Subject incidence of treatment-emergent adverse events and serious adverse events.
Exploratory	

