5.3 Demographics and Baseline Related Definitions

Age

Age is the subject's age in years at enrollment as recorded on the eCRF.

Baseline Lipid and Lipid-related Parameters

Baseline values for LDL-C, triglycerides and troponin are defined as the concentrations measured through **local lab at screening**. **Baseline values for other lipids (eg, total cholesterol, HDL-C and VLDL-C), ApoA1, ApoB, Lp(a) and their derived parameters (eg, ratio between them) are defined as the concentrations measured through central lab on Study Day 1.**

Baseline Laboratory Variables

Baseline values for laboratory variables are defined as the assessment measured at screening.

Baseline Concomitant Medication Usage and Medical History

Baseline values for background statin therapy, lipid-modifying concomitant medication usage and medical history are defined as the assessment measured at screening. For concomitant medication that is not lipid-modifying baseline is defined as measurement at study day 1.

Baseline Image Data

Baseline values for OCT, IVUS image data are defined as the assessment measured at screening.

Baseline Vital Signs

Baseline values for vital signs are defined as the last non-missing value collected prior to or on Study Day 1.

Change (absolute change) from Baseline

The arithmetic difference between a post-baseline value and baseline for a given time point:

Change (absolute change) from baseline = (post-baseline value – baseline value).

Percent Change from Baseline

The percent change from baseline for a given variable at a given time point is defined as:

$100 \times [(value \text{ at given time point} - baseline \text{ value}) / baseline \text{ value}]$.

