9.5 Efficacy Analyses

Endpoint	Primary Analysis	Sensitivity Analysis	Multiplicity Adjustment
Primary Endpoint			To preserve the family wise type 1 error rate at 0.05 for testing the primary and secondary endpoints, the primary analysis of primary endpoint will be tested first. If the treatment effect from the primary analysis of the primary endpoint is significant at a two-sided significance level of 0.05, the secondary endpoints will be tested with two-sided significance level of 0.05 using the Hochberg method.
Absolute change in minimum FCT from baseline to week 50	Multiple Imputation + ANCOVA (FAS)	Quade Test (FAS) COVID-19 Impact Analysis	
Secondary Endpoints			
Coronary artery based: 
 Percent change in minimum FCT in a matched segment of the artery as determined by OCT from baseline to week 50. Absolute change in mean minimum FCT for all images accessed in an individual subject as determined by OCT from baseline to week 50. Absolute change in the maximum lipid arc in a matched segment of artery as determined by OCT from baseline to week 50. Plaque-based: 
 Absolute change in minimum FCT, maximum lipid arc, and lipid core length in lipid rich plaques defined as minimum FCT < 120µm 	Multiple imputation + ANCOVA (FAS)	NA	

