9.5.1 Analyses of Primary Efficacy Endpoint(s)

Primary Analysis:

To assess the primary endpoint of absolute change in minimum FCT from baseline to week 50, an ANCOVA (Analysis of Covariance) model on the FAS will be used, including terms for treatment group, stratification factor (current statin use [> 4 weeks or ≤ 4 weeks] at screening), baseline minimum FCT as covariates. Least square means and corresponding 95% confidence intervals (CI) will be calculated for each treatment group and for the difference between treatment groups. For subjects with missing post-baseline **minimum FCT**, the **post-baseline minimum FCT value** will be imputed

using multiple imputation. The imputation model will include treatment group, stratification factor, baseline LDL-C, baseline minimum FCT, age as covariates. **At least** five imputations will be conducted, and each complete dataset after imputation will be analyzed using the ANCOVA model. SAS PROC MIANALYZE will be used to combine the results from individual ANCOVA models.

Sensitivity Analysis

- 1) Non-parametric analysis (Quade test) will be performed on FAS as sensitivity analysis. The missing data will be imputed using multiple imputation. **The imputation model and the analysis approach of combining results from multiple imputed datasets will be same as the primary analysis.**
- 2) **COVID-19 Impact sensitivity analysis:**
To determine the impact of COVID-19, a sensitivity analyses will be conducted. All the available post-baseline FCT values will be considered in the analysis, irrespective of the analysis visit window (ie, the post-baseline FCT values after week 56 will also be considered for the analysis). The ANCOVA model for COVID-19 Impact analysis will include the covariates of treatment group, stratification factor (current statin use [> 4 weeks or ≤ 4 weeks] at screening), baseline minimum FCT as covariates. The imputation method, model and analysis approach will be same as the primary analysis.

Covariate and Subgroup Analysis

In addition to the primary analysis, covariate adjusted analysis of the primary efficacy endpoint will be performed as supportive analyses using the baseline covariates in [Section 4.1](#), in their original format, one at a time, in the ANCOVA model used in the primary analysis.

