9.5.2 Analyses of Secondary Efficacy Endpoint(s)

The secondary efficacy endpoints will be analyzed using the similar method as used in primary analysis of the primary efficacy endpoint but adjusting for corresponding baseline variable. The Hochberg method for multiplicity adjustment will be used to maintain the overall error rate at 0.05.

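### Does SAP 8.6, which calls for an unnamed alternative method if assumptions fail, leave the confirmatory test of the six secondary endpoints undefined?

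*SAP*

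**What the plan says.** SAP 8.6, within the section on data screening, says: "If the distributional assumptions are not met, then alternative methods will be utilized". It adds: "The use of alternative methods will be fully justified in the CSR". It applies to all endpoints alike.

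The efficacy sections are specific. In the SAP 9.5 table, the primary-analysis column gives multiple imputation plus ANCOVA on the full analysis set for the primary endpoint and again for the secondary endpoints. The sensitivity column lists the Quade test and a COVID-19 analysis for the primary endpoint, and NA for the secondaries. SAP 9.5.2 says the secondary endpoints "will be analyzed using the similar method as used in primary analysis of the primary efficacy endpoint", each with its own baseline as covariate. Protocol 10.3.2.2 also names ANCOVA for them.

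The nonparametric method belongs to the primary endpoint only. The protocol says "A sensitivity analysis of the primary endpoint will be conducted using nonparametric method and FAS", and SAP 9.5.1 says "Non-parametric analysis (Quade test) will be performed on FAS as sensitivity analysis".

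SAP 2.1 lists six secondary endpoints, three segment-based and three plaque-based. The first is "Percent change in minimum FCT in a matched segment of artery as determined by OCT from baseline to week 50". Under SAP 9.1 all six enter a Hochberg procedure at 0.05 once the primary endpoint is significant.

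**The concern.** The secondary endpoints form a confirmatory family, so a reader should be able to tell from the SAP which p-values enter the Hochberg step. SAP 8.6 is worded as an obligation, whereas SAP 8.5 only says that outlier sensitivity analyses may be done. If a residual check failed for a secondary endpoint, 8.6 would call for another method, 9.5 would list ANCOVA, and no fallback is named for that endpoint. Nothing dates the choice before the unblinding described in SAP 7.2.

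The case is not remote. Absolute and percent change in the same minimum FCT are both analysed by ANCOVA, and they cannot both have constant variance unless every subject has the same baseline. Because Hochberg is a step-up procedure, a change of method for one endpoint can also move the verdict on others. At stake would be a list of confirmed secondary endpoints that depends on an unrecorded choice.

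**Working it through.** **Planning figures.** No stated number is in dispute. With effect 50.97 µm, SD 86 µm, two-sided 0.05 and 90% power, n per arm = 2 × (1.960 + 1.282)² × (86/50.97)² = 59.8, so 60 by the normal approximation and 61 by the t-test (122 in all). The plan has 150 × 5/6 = 125 analysed. Power with 62 and 63 analysed is 90.8%.

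**Is a failed check foreseeable?** Let absolute change have constant SD s.
- SD of percent change at baseline b is 100 × s/b. Between 65 µm (the risk value in Protocol 3.2.2) and 120 µm (the ceiling in Protocol 6.1) the variance ratio is (120/65)² = 3.41. These are two reference values, not a baseline distribution.
- Percent change cannot fall below −100%. At b = 120 and s = 86 its SD is 71.7 points. A normal model puts Φ((−100 − 42.5)/71.7) = 2.3% of subjects below the floor if mean change is 50.97 µm, and Φ(−100/71.7) = 8.1% if it is 0.
- In simulation with normal errors, percent change failed a 5% check of normality or constant variance in 84–99% of trials, against 9–11% for absolute change. Normality alone failed in 17–50%.

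So the trigger is likely to be met for percent change.

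**Can one endpoint move the others?** The Hochberg thresholds for six endpoints, from the largest p-value down, are 0.05, 0.025, 0.0167, 0.0125, 0.01 and 0.0083. With five p-values of 0.03 and a sixth of 0.04, the largest is below 0.05 and all six are rejected. With a sixth of 0.06, that value exceeds 0.05 and each 0.03 exceeds its own threshold, so none is rejected. The example is correct but constructed.

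**Does the error rate suffer?** Familywise error with six true nulls (4000–5000 trials per cell, Monte Carlo SE about 0.3 points):

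| Rule | Familywise error |
|---|---|
| ANCOVA throughout | 3.5–4.8% |
| Quade throughout | 3.5–4.3% |
| Switch triggered by distribution | 3.5–4.6% |

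A separate run on percent change alone used 62 and 63 subjects, log-normal follow-up, no imputation or strata, and 6000 trials per cell. ANCOVA rejected a true null in 4.1–5.5% of trials. Taking the better of ANCOVA and Quade after seeing results gave 6.0–7.7% for that endpoint, but 8.6 does not allow this: its trigger is the distribution, not the p-value.

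**How often would the confirmed set change?** Effects were set at 50.97/86 = 0.593 SD or half of that (1500 trials per cell). Switching percent change alone altered the set in 4–14% of trials and altered another endpoint's verdict in 0.6–3.7%. Switching all six gave 19–24% (normal errors) and 28–37% (skewed errors), but foreseeability is shown for one endpoint only, so those are not the matching figures. All effects were real in these runs, so the extra rejections are true positives.

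**Limits of the simulation.** The six-endpoint runs assume 150 randomised, 25 missing completely at random, 10 imputations, baseline mean 60 and SD 18 µm, mean change 40 µm, SD of change 86 µm, and five generic endpoints with correlation 0.3 or 0.6. With normal errors the placebo follow-up then has mean 60 + 40 = 100 and SD about √(86² + 18²) = 87.9, so about Φ(−100/87.9) = 13% of values are negative, which is impossible. With gamma errors, which keep follow-up positive, absolute change at SD 86 also failed the checks in 99–100% of trials.

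**What would a firmer rule gain?** Locking ANCOVA confirms 4.9 of 6 endpoints on average with normal errors (Quade 4.7–4.9) and 4.9–5.0 with skewed errors (Quade 5.4–5.5). A switch recovers about half an endpoint under skew, but judges that endpoint on a rank test that gives no mean difference. A blinded switch that leaves treatment out of the model does not work well either. At SD 22 the arms differ by 50.97/22 = 2.3 SD, and the check fired on exactly normal absolute change in 28–31% of trials, because the residuals are then a mixture of two arms.

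**The case for a change.** The strongest case for a change is that a confirmatory family should be reproducible from the SAP alone. The clause is mandatory in wording, its trigger is likely to be met for at least one endpoint, the choice is not dated before unblinding, and one sentence would settle it. The facts behind this stand: 8.6 names no method and does not say which p-value counts.

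The step from there to rival confirmatory tests does not hold. SAP 8.6 says that alternatives will be used; it does not say that they replace the listed analysis or feed the Hochberg step. It makes no distinction between primary and secondary endpoints, and for the primary endpoint nobody doubts that 9.5 governs, with ANCOVA decisive and Quade as support. At the planning SD with positive follow-up values, absolute change fails the same checks, so the primary endpoint faces the same trigger and the specific text still settles it. The same table column gives the same analysis for the secondaries. Protocol 10.3.2.2 agrees, and SAP section 10 declares no change from the protocol's analyses. Any alternative must also be justified in the study report, where a reader would see it beside the ANCOVA result.

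The NA entry is not a fault either. Neither document requires sensitivity analyses for secondary endpoints, and adding Quade for all six is a preference.

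**Conclusion.** The wording of 8.6 is loose, but no change to the plan is needed. An analyst following SAP 9.5 and 9.5.2 would take the Hochberg p-values from multiple imputation plus ANCOVA and report any alternative as support. A sentence saying so would only restate what those sections list. On the simulated evidence ANCOVA, Quade and a distribution-triggered switch all keep familywise error below 5%, so conclusions stay sound under any of them. Whether to lock ANCOVA or allow a switch is a fair trade-off: about half an endpoint of power under skewed errors against a mean difference on the planned scale.

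The remaining effect is limited to the list of confirmed secondaries: 4–14% of trials if percent change alone were switched, with another endpoint affected in 0.6–3.7%. These figures depend on assumed baselines, error shapes, effects and correlations, and part of the normal-error setting is not physically possible. The primary endpoint and the sample size are unaffected.

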8.7 Validation of Statistical Analyses

Programs will be developed and maintained, and output will be verified in accordance with current risk-based quality control procedures.

Tables, figures, and listings will be produced with validated standard macro programs where standard macros can produce the specified outputs.

The production environment for statistical analyses consists of Amgen-supported versions of statistical analysis software; for example, the SAS System version 9.4 or later.

9. Statistical Methods of Analysis

9.1 General Considerations

Summary statistics for continuous variables will include the number of subjects, mean, median, SD or standard error, minimum, and maximum. For categorical variables, the frequency and percentage will be given.

Statistical inferences will be provided for analyses of primary and secondary efficacy endpoints. Unless specified otherwise, all statistical tests are 2-sided with a significance level of 0.05; no statistical inference and imputation will be conducted for analyses of safety endpoints. No imputation will be conducted for analyses of exploratory endpoints. Even though the p-values will be generated for exploratory endpoints, they are descriptive in nature.

Multiplicity Adjustment Method

To preserve the family wise type 1 error rate at 0.05 for testing the primary and secondary endpoints, the primary analysis of primary endpoint will be tested first. If the treatment effect from the primary analysis of the primary endpoint is significant at a significance level of 0.05, the secondary endpoints will be tested with significance level of 0.05 using the Hochberg method.

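### Naming Hommel instead of Hochberg for the six secondary endpoints would be a cheap, small gain in power; Hochberg itself is valid

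*SAP*

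**What the plan says.** The multiplicity rule is the same in Protocol 10.3.2.1 and in SAP 9.1, 9.5 and 9.5.2. The aim in SAP 9.1 is: "To preserve the family wise type 1 error rate at 0.05 for testing the primary and secondary endpoints". The primary endpoint acts as a gate ("If the treatment effect from the primary analysis of the primary endpoint is significant at a significance level of 0.05"), after which "the secondary endpoints will be tested with significance level of 0.05 using the Hochberg method". The table in SAP 9.5 adds that the level is two-sided, and SAP 9.5.2 repeats the choice: "The Hochberg method for multiplicity adjustment will be used to maintain the overall error rate at 0.05".

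SAP 2.1 lists six secondary endpoints. Three are segment-based: percent change in minimum fibrous cap thickness (FCT), change in mean minimum FCT, and change in maximum lipid arc. Three are plaque-based, given in SAP 9.5 as "Absolute change in minimum FCT, maximum lipid arc, and lipid core length in lipid rich plaques".

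Neither document says why Hochberg was chosen, states a dependence assumption, or sets a power target for the secondary endpoints.

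**The concern.** Hochberg is a conservative shortcut of the closed Simes test, and Hommel carries out that closed test in full. The standard proof of error control for both rests on the Simes inequality for each intersection of hypotheses. Under that condition both hold the family-wise error at 5%. Hommel rejects everything that Hochberg rejects, and sometimes more.

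The six secondary endpoints carry the only confirmatory efficacy claims beyond the primary, because SAP 9.1 treats exploratory p-values as descriptive. At stake is an occasional secondary claim that the data would support at the same nominal error rate but that the chosen procedure does not reach.

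**Working it through.** **Inputs from the documents.** Two-sided level 0.05 and a primary-first gate (SAP 9.1); six secondary hypotheses (SAP 2.1); for the primary, difference 50.97 µm, SD 86 µm, 1 in 6 not evaluable, 150 randomised, 90% power (SAP 3.2).

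**The plan's own figure.** By the normal approximation, n per arm = 2(1.960 + 1.282)² × (86/50.97)² ≈ 60. The t-test needs 61 per arm, or 122 analysed. With 125 analysed (62.5 per arm) its power is 90.8%, and 125/(1 − 1/6) = 150. The sample size reproduces. It concerns the primary only; the documents state no figure for the secondary family. A 90% power corresponds to a non-centrality of 1.960 + 1.282 ≈ 3.24, which is used below.

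**The two rules**, for ordered p-values p(1) ≤ … ≤ p(6):
- Hochberg: find the largest i with p(i) ≤ 0.05/(6 − i + 1) and reject hypotheses 1 to i.
- Hommel: find the largest j such that p(6 − j + k) > k × 0.05/j for every k = 1, …, j. Reject every p ≤ 0.05/j, or reject all six if no such j exists.

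**A near-worst-case illustration:**

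| Rank | p | Hochberg cut-off | Hommel-adjusted p |
|---|---|---|---|
| 1 | 0.009 | 0.0083 | 0.036 |
| 2 | 0.011 | 0.0100 | 0.037 |
| 3 | 0.015 | 0.0125 | 0.042 |
| 4 | 0.020 | 0.0167 | 0.042 |
| 5 | 0.028 | 0.0250 | 0.056 |
| 6 | 0.060 | 0.0500 | 0.060 |

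Every p-value just misses its Hochberg cut-off, so Hochberg rejects 0 of 6. For Hommel, j = 6, 5, 4 and 3 fail. At j = 2 the condition holds (0.028 > 0.025 and 0.060 > 0.050), so every p ≤ 0.05/2 = 0.025 is rejected: 4 of 6.

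The three largest p-values show where the difference arises. Simes cut-offs for a triple are 0.0167, 0.0333 and 0.05, and 0.028 passes the second. Hochberg's corresponding cut-offs are 0.0167, 0.025 and 0.05, and nothing passes.

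**How often it matters.** Simulation, 400,000 replicates per scenario, six two-sided tests with a common correlation and equal power for all six. Powers and correlations are assumptions. The primary gate is not yet applied.

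| Power of each test | Correlation | Mean rejections, Hochberg → Hommel | Trials with an extra claim | Chance of any claim, Hochberg → Hommel |
|---|---|---|---|---|
| 50% | 0 | 1.757 → 1.819 | 5.0% | 82.2% → 83.6% |
| 50% | 0.8 | 2.089 → 2.156 | 4.4% | 46.1% → 48.0% |
| 70% | 0 | 3.308 → 3.373 | 5.2% | 97.1% → 97.6% |
| 70% | 0.8 | 3.408 → 3.475 | 4.5% | 68.0% → 69.8% |
| 80% | 0.5 | 4.164 → 4.213 | 3.7% | 90.0% → 90.8% |
| 90% | 0 | 5.206 → 5.218 | 1.1% | almost 100% for both |
| 90% | 0.8 | 5.012 → 5.052 | 2.6% | 89.9% → 90.9% |

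With three endpoints at 90% power and three null (correlation 0.5), the mean goes from 2.314 to 2.327. With one at 90% and five null, extra claims occur in 0.2% to 0.4% of trials. Hommel lost a rejection in no replicate, and the chance of rejecting all six did not change.

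**With the gate.** Allowing secondary claims only when a primary with 90% power is significant, and taking equal non-centralities of 1.5 to 3.24 and correlations of 0 to 0.8, an extra claim occurs in about 1% to 5% of trials. The chance of any secondary claim rises by 0 to about 2 points, and the mean gain is at most about 0.07 of six. If the primary is only as strong as the secondary endpoints (correlations 0.5 to 0.8), the first two figures fall to 1.7% to 3.3% and 0.5 to 1.2 points.

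**Error under the global null** (ungated, correlations 0 to 0.8): 2.9% to 4.9% for Hochberg and 3.2% to 4.9% for Hommel, all below 5%.

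**The case against.** The strongest reply is that nothing is broken. Hochberg after a primary gate meets the plan's stated aim, is pre-specified, and reads the same in protocol and SAP. No secondary power target exists to be missed. All of this stands, and it makes the point an optional refinement.

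A reader might infer that the plan throws away secondary claims for no return. The documents and figures do not support that. In most simulated trials the two procedures reject the same hypotheses, and the 0-of-6 against 4-of-6 example was built so that each p-value narrowly misses its cut-off. Hochberg also buys something: its critical values never exceed the Simes values, so it keeps some margin if the Simes inequality fails, and it is simpler to apply and explain. The simulated error rates cover the global null under common correlations only, so they do not prove control under every dependence structure.

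A reader might also infer that, because the six endpoints come from the same images and are closely related, this trial is especially exposed. That does not follow. At a non-centrality of 2.0 the share of trials with an extra claim falls from 5.1% at correlation 0 to 4.4% at 0.8. Only the gain in the chance of any claim tends to rise with correlation, to about 2 points.

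Finally, the rule is in the protocol, and Protocol Appendix 3 sends amendments to ethics committees. Changing only the SAP would make the statement in SAP section 10, that nothing departs from the protocol, untrue. This is a real cost, and the fix has to deal with it.

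**Conclusion.** This holds as a cheap improvement and not as an error. That Hommel never rejects fewer hypotheses is a mathematical fact and does not depend on the assumed effects. Its size does: the gated figures above rest on assumed non-centralities and correlations and on a primary powered at 90%. If every secondary endpoint were as well powered as the primary, extra claims would occur in only about 1% to 2.5% of trials. The sample size, the primary test and its 90% power are unaffected. Keeping Hochberg would be defensible, preferably with a sentence giving the reason.

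**What to change.** Before database lock and unblinding, replace the Hochberg method by the Hommel method in SAP 9.1, 9.5 and 9.5.2. State that it is applied to the six pooled two-sided p-values from the multiply imputed analyses, after the primary gate, and that Hommel-adjusted p-values will be reported. Either align Protocol 10.3.2.1 or list the change, with its rationale, in SAP section 10.

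The cost is a method name in three SAP sections plus one documented departure from the protocol. No data, patients or sample-size change are needed, and standard software computes Hommel from p-values alone. The downsides are a procedure that is harder to follow by hand and a smaller margin than Hochberg's if the Simes inequality fails. If unblinding has already taken place, leave Hochberg as specified.
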